4.2 Kappa test

Kappa test will be used to analyze the equivalence of test reagent and comparison method. Using statistical software, Kappa test will be used to compare the results of investigational reagents with gold standards, and k value will be calculated. When $k > 0.75$, the investigational reagent and comparison method show good consistency.

$$Kappa = \frac{P_a - P_c}{1 - P_c}, \text{ where } P_a = \frac{A + D}{N}, P_c = \frac{(A + B)(A + C)}{N} + \frac{(B + D)(C + D)}{N}$$

5 Quality Control Method

Quality control should be applied at every stage of the clinical trial to ensure that all data are reliable and correct. The quality control method is as follows:

(1) Qualifications of researchers involved in the study: Researchers involved in the clinical trial must have professional expertise, qualifications and competences in the clinical trial, and pass the qualification examination, and staffing should be relatively fixed.

(2) Training and preliminary tests: The sponsor is responsible for the training of researchers before the start of clinical trial, so as to help clinical researchers fully understand the clinical trial protocol, the detection of investigational products, the filling of original records and forms, etc.

(3) Laboratory quality control: Clinical laboratories should be strictly in accordance with the *Measures for the Administration of Clinical Gene Amplification Testing Laboratories in Medical Institutions* (MOH Office MA [2010] No. 194 or the current effective version) and other relevant administrative regulations of molecular biology laboratories and clinical gene amplification laboratories.

(4) Only when the quality control of investigational products meets relevant requirements can the test data be valid.

(5) Clinical trial monitoring: The monitor shall make a complete monitoring plan

before the start of the clinical trial, and monitor the clinical trial according to the monitoring plan to ensure that the clinical trial is carried out according to the clinical protocol, and ensure the intactness and accuracy of the original test data and records.

6 Provisions for Protocol Amendment

Any modification of the protocol during the trial shall be explained, and the time, reason, process and filing of the change shall be elaborated in detail, and its influence on the evaluation of the overall study results shall be demonstrated. If the investigators modify the protocol and case report form during the trial, it must be approved by the ethics committee before continuing the clinical trial.

7 Ethical issues and explanations involved in the clinical trial

The purpose of this clinical trial is to evaluate the performance of human PDGFRA gene D842V mutation detection kit (PCR-fluorescence probe method) in clinical application. The samples used in this clinical trial are the remaining pathological specimens detected during the treatment. These samples are only used for in vitro diagnosis without direct contact with patients and any harm to patients. These sample are only used to compare performance of the test reagent and the comparison method. The test results are only used for research and analysis related to this test, and will not guide the diagnosis and treatment of patients, therefore it will not have any adverse effects on human body. Informed consent can be exempted after being approved by the Ethics Committee.

This clinical trial is conducted in strict accordance with the *Declaration of Helsinki*, and the validation of this clinical trial involves relevant data of patients. For example: The patient's unique traceable number, age, sex, pathological diagnosis results, etc. The patient's relevant data will be kept confidential by the hospital and Genetron Health (Beijing) Co., Ltd, and the implementing party and verifier of the clinical trial are committed not to disclose the contents related to the subject specimens.

8 Data Processing and Record Storage

Investigators should record all the items on the clinical trial case report form truthfully, in detail and carefully according to the filling requirements, so as to ensure that the contents in the form are complete, true and reliable. All observations and findings obtained from the clinical trial should be verified to ensure the reliability of data and ensure that all conclusions in clinical trials come from original data. The clinical trial personnel should truly fill in relevant clinical information and the test results of clinical trials, and have them reviewed and signed by a specially-assigned person.

All original data records generated by this clinical trial shall be filed and preserved by the clinical sites, and the retention period shall be determined by the sites, but shall not be less than 5 years upon the completion of the clinical trial.

9 Responsibilities of Involved Parties

1. Sponsor's responsibility:

- (1) Work with medical institutions to design and formulate clinical trial protocols, and sign clinical trial protocols and contracts agreed by both parties;
- (2) Provide medical institutions with tested products and required contrast reagents free of charge, and provide necessary test equipment;
- (3) Provide training for study staff.

2. Test facility's responsibility:

- (1) Should be familiar with the relevant information provided by the implementing party and familiar with the use of the tested products;
- (2) Work with the implementing party to design and formulate clinical trial protocols, and sign the clinical trial protocols between both parties;
- (3) Propose clinical trial reports and be responsible for the correctness and reliability of the reports;
- (4) The information provided by the implementing party shall be kept confidential, and the test results and process shall not be disclosed to any third party.

10 Study Technology Roadmap

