The full name of the protein encoded by PDGFRA gene is platelet derived growth factor receptor alpha α . As a cell surface receptor tyrosine kinase, PDGFRA can be activated after binding with its corresponding ligand PDGF, and then activate the phosphorylation pathways of phosphatidylinositol, cAMP and various proteins to regulate cell division and proliferation. Abnormal gene activation may cause tumorigenesis and promote tumor angiogenesis. PDGFRA mutation is closely related to GIST. Currently, up to 85% of patients with GIST have PDGFRA or KIT gene mutations. These mutations are associated with the production of abnormal KIT and PDGFRA proteins, which drive cancer. The two proteins can usually be shut down by imatinib (Glivec) and similar drugs, so as to block the activity of proteins. However, the PDGFRA Exon 18 mutant is very special. It changes the shape of PDGFRA protein, thus preventing the protein from binding to drugs. Meanwhile, clinical studies found that Avapritinib was able to bind to all mutated PDGFRA proteins tested and inhibit their activity in cancer cells. Since the most common mutant of PDGFRA is D842V mutant on Exon 18, the qualitative detection of D842V mutant on PDGFRA

in patients with GIST can be used to assist the concomitant diagnosis of Avapritinib in clinical drug treatment.

Genetron D842V PCR Kit is used for qualitative detection of D842V mutation in Exon 18 of PDGFRA gene in formalin-fixed paraffin-embedded (FFPE) tissue samples of patients with gastrointestinal stromal tumors (GIST), and for concomitant diagnosis of Avapritinib tablets in drug therapy. The result of this kit is for the related sites only, used as a reference for clinicians to choose proper tumor-targeted drugs for patients with GIST, and cannot be used as the only basis for individualized treatment of patients. Clinicians should thoroughly evaluate the detection results based on factors such as patients' condition, drug indications, treatment response and other laboratory indicators.

2 Study Purpose

The primary purpose of this study is to validate and evaluate the safety and effectiveness of Genetron D842V PCR Kit by comparing the results of this kit to those of the simultaneous detection with Sanger sequencing method, calculating the coincidence rate and consistency between the test reagent and the comparison method.

3 Study Design

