3.2 Sample Screening

3.2.1 Basis to Determine Sample and Sample Size

$$n = \frac{\left[Z_{1-\alpha/2} \sqrt{P_0(1-P_0)} + Z_{1-\beta} \sqrt{P_T(1-P_T)} \right]^2}{(P_T - P_0)^2}$$

Where, n represents the sample size; $Z_{1-\alpha/2}$ and $Z_{1-\beta}$ are fractions of standard normal distribution, P_0 is the target value of the evaluation indicator, and P_T is the expected value of the evaluation indicator for in vitro diagnostic reagents.

According to the results of preclinical studies, the target value of positive coincidence rate between test reagent and contrast reagent is up to 85% with the expected value up to 99%, the minimum sample size of positive control group is estimated to be 32 cases; if the target value of negative coincidence rate is up to 85% with the expected value up to 90%, the minimum sample size of negative control group is estimated to be 363 cases.

This product is classified as Class III IVD reagent medical device, and the overall sample size of clinical trials should meet the requirements of current relevant laws and regulations. According to the Measures for the *Administration of Registration of In-Vitro Diagnostic Reagents* (CFDA [2014] No. 5) and the *Technical Guidelines for Clinical Trials of In-Vitro Diagnostic Reagents* (CFDA [2014] No. 16), the overall sample size of this clinical trial should not be less than 1,000. It is planned to carry out the trial in at least three clinical sites, with the enrollment of no less than 300 samples at each site. In case of objective reasons, when the sample size is insufficient, appropriate adjustments can be made among the sites to ensure the overall sample size. If the relevant laws and regulations change during the trial, the latest laws and regulations shall prevail, and the number of positive and negative control samples should be statistically significant.

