4.1 Positive, Negative and Total Coincidence Rates Between Test Reagent and Comparison Method

For each genetic locus, fourfold tables will be used to calculate the positive and negative coincidence rates, positive and negative predictive values, total coincidence rate and their 95% confidence intervals. Using statistical software, Kappa test is used to determine statistical significance of the two detection methods.

Table 1 Result Summary of Clinical Trial Comparing Test Reagent and Comparison Method

Test Reagent	Comparison Method		Total
	Positive	Negative	
Positive	A	B	A+B
Negative	C	D	C+D
Total	A+C	B+D	A+B+C+D

Samples with mutant genotype detected are considered as positive, and samples without mutant genotype are considered as negative.

The calculation formula is:

$$\text{Positive coincidence rate} = A/(A+C) \times 100\%$$

$$\text{Negative compliance rate} = D/(B+D) \times 100\%$$

$$\text{Positive predictive value (PPV)} = A/(A+B) \times 100\%$$

$$\text{Negative predictive value (NPV)} = D/(C+D) \times 100\%$$

$$\text{Total coincidence rate} = (A+D)/(A+B+C+D) \times 100\%$$

The calculation formula of 95% confidence interval: $p \pm 1.96 \times [p(1-p)/n]^{1/2}$ (where P

represents positive and negative coincidence rates, positive and negative predictive values and total coincidence rate, n presents the sample size. If $p > 0.9$, Wilson score method will be used for correction).

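### The sample size rests on an 85% target for each coincidence rate, but equivalence is assigned to kappa above 0.75, which can contradict that target in both directions

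*Protocol*

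**What the plan says.** Section 2 makes the study purpose a comparison with Sanger sequencing by "calculating the coincidence rate and consistency between the test reagent and the comparison method".

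Section 3.2.1 of the protocol sizes two separate comparisons with a single-proportion formula:

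- Positives: "the target value of positive coincidence rate between test reagent and contrast reagent is up to 85% with the expected value up to 99" (per cent), from which "the minimum sample size of positive control group is estimated to be 32 cases".
- Negatives: "if the target value of negative coincidence rate is up to 85% with the expected value up to 90" (per cent), which leads to 363 cases.

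The section adds, on regulatory grounds, that "the overall sample size of this clinical trial should not be less than 1,000". It does not fix how many of the 1,000 are positive.

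Section 4.1 calculates both rates with 95% confidence intervals: Wald by default, with the condition "If $p > 0.9$, Wilson score method will be used for correction". It does not compare any rate or limit with 85%.

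Section 4.2 then states: "Kappa test will be used to analyze the equivalence of test reagent and comparison method". Its only numerical rule is "When $k > 0.75$, the investigational reagent and comparison method show good consistency". The rule applies to the calculated value; no confidence limit for kappa is used.

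**The concern.** The quantity that justifies the sample size plays no part in the stated conclusion, and the quantity that carries the conclusion was not used for sizing. Kappa combines both kinds of error and weights them by the share of positives. The same 0.75 is therefore demanding on false positives when positives are rare, yet tolerant of missed positives when false positives are few.

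Two wrong outcomes are possible. A kit whose positive rate is shown to be below 85% can still be called consistent. This is the more serious one, because the kit is meant to identify patients for a targeted drug. In the other direction, a kit that performs exactly as planned and clears 85% on both rates can be denied the label.

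**Working it through.** **Inputs.** From Section 3.2.1: target 85%; expected 99% (positive) and 90% (negative); minima 32 and 363; total at least 1,000. From Section 4.1: the interval formulas. From Section 4.2: the 0.75 cut-off. Assumed: two-sided alpha 0.05 and 80% power, which the protocol does not state. Splits shown are 32+363 (the two minima) and 32+968 (the minimum number of positives within 1,000), with others where noted.

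**1. The protocol's own figures.** n = [1.960·√(P0(1−P0)) + 0.842·√(PT(1−PT))]² / (PT−P0)². With 0.85 and 0.99 this gives 31.3, so 32. With 0.85 and 0.90 it gives 362.8, so 363. Both match.

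**2. Kappa.** κ = (Pa − Pc)/(1 − Pc), with Pa = (A+D)/N and Pc = [(A+B)(A+C) + (B+D)(C+D)]/N². Section 4.2 as extracted shows the divisor N rather than N². That may be a loss in reading the PDF, and nothing here depends on it.

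**3. Too lenient.** Take 21/32 detected, one false positive, 968 negatives: A=21, B=1, C=11, D=967.

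- Pa = 988/1000 = 0.988
- Pc = (22×32 + 968×978)/1000² = 0.9474
- κ = 0.0406/0.0526 = 0.772 (0.762 with 363 negatives)
- Positive rate 65.6%; Section 4.1 interval 65.6 ± 1.96·√(0.656×0.344/32) = 49.2% to 82.1%; Wilson 48.3% to 79.6%

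Both intervals lie wholly below 85%, yet kappa passes. With no false positives the same happens at every split tried. At 500+500, for example, 376/500 (75.2%, interval 71.4% to 79.0%) gives κ = 0.752.

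Chance of κ > 0.75 with 32+968, summed over exact binomial distributions:

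| True positive rate | Negative rate 100% | 99.9% | 99.5% | 99% |
|---|---|---|---|---|
| 70% | 87% | 80% | 51% | 17% |
| 80% | 99% | 99% | 88% | 53% |

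**4. Too strict.** At the planned 99%/90% with 32+968, the expected counts are A=31.68, B=96.8, C=0.32, D=871.2.

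- Pa = 0.9029; Pc = (128.48×32 + 968×871.52)/1000² = 0.8477
- κ = 0.0551/0.1523 = 0.36 (0.59 with 32+363)

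Even with 32/32 detected, κ > 0.75 allows at most 18 false positives in 363 (negative rate 95.0%) or 20 in 968 (97.9%). A true 90% negative rate produces about 36 or 97.

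Chance of κ > 0.75 with a true positive rate of 99%:

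| True negative rate | 32+363 | 32+968 |
|---|---|---|
| 90% (planned) | 0.03% | about 0 |
| 95% | 51% | about 0 |
| 97% | 98% | 4% |
| 98% | >99.9% | 56% |
| 99% | about 100% | 99.7% |

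**5. Dependence on case mix.** At N = 1,000 and 99%/90%, the chance of κ > 0.75 is 13%, 53% and 91% with 150, 173 and 200 positives. With all positives detected, the negative rate needed falls from 97.9% (32 positives) to 93.8% (100), 90.9% (150) and 88.2% (200).

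**6. Direct conflict with an 85% rule.** With 34+966 at 99%/90%, both Wilson lower limits exceed 85% while κ ≤ 0.75 in 95% of trials. At 70%/99.9%, κ > 0.75 while the 85% rule fails in 83% of trials.

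**The case against.** The best counter-argument is that the protocol never says the kit passes or fails on kappa alone. It names both coincidence rate and consistency as its purpose and gives each rate a target and an interval. A reader could judge all of them together, and a result of 21/32 would be printed beside its interval. The statistical analysis plan, which is not available here, might also compare the rates with 85%. On that view a sentence stating which measure governs would be enough.

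Part of this stands: the text never makes kappa sufficient by itself, and the reported rate would be visible. But Section 4.2 does assign equivalence to kappa, and 0.75 is the only threshold in the analysis section. A plan that added an 85% rule would still conflict with that sentence. Requiring both criteria would remove the lenient failure but keep the strict one.

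Three further points are fair:

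- The strict failure depends on the case mix and on the 90% sizing assumption. It largely disappears with 200 positives or a 99% negative rate. But few false positives is exactly the condition for the lenient failure.
- The 32+363 split falls below the 1,000 floor. It is shown because those are the protocol's derived minima.
- Section 4.1 also mentions a kappa test of statistical significance. That does not remove the dependence on case mix.

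**Conclusion.** The concern holds. The protocol sizes on one criterion and fixes another for equivalence, and the two can give opposite answers. With 32 positives, kappa above 0.75 is compatible with a positive coincidence rate of 65.6% whose interval ends at 82.1%. At the planned 99%/90%, the chance of exceeding 0.75 is 0.03% (32+363) or about zero (32+968).

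The lenient failure was found at every split tried from 32+363 to 500+500, provided false positives are few. The strict failure at the planned rates applies when positives are below roughly 15% to 20% of 1,000. The results rest on the standard kappa formula and on independent samples; the split is an assumption because the protocol leaves it open. This should be corrected in the protocol.

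**What to change.** Replace the 0.75 sentence in Section 4.2 with:

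> Agreement is concluded if the lower limits of the two-sided 95% Wilson confidence intervals for both the positive and the negative coincidence rate exceed 85%. Wilson limits are used for this decision at all values of p. Kappa with its 95% confidence interval is supportive only.

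Using Wilson throughout matters. The switch in Section 4.1 would pass 321/363 on a Wald limit of 85.1%, where Wilson gives 84.7%, and the one-sided type I error would be 3.6%.

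In Section 3.2.1, restate the power under this rule, including joint power, and the minimum number of positives. The figures would be:

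| Group | Needed to pass | Power at planned rate | One-sided type I error at 85% |
|---|---|---|---|
| 32 positives | 32/32 (31/32 has limit 84.3%) | 0.99³² = 72% | 0.85³² = 0.6% |
| 34 positives | 33/34 (limit 85.1%) | 95% | 2.8% |
| 35 positives | 34/35 (limit 85.5%) | 95% | 2.4% |
| 363 negatives | 322 | 82% | 2.5% |
| 968 negatives | 845 | 99.7% | 2.4% |

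Joint power, as the product under independence, is 59% at 32+363, 72% at 32+968, 78% at 34+363, and 95% at 34+966 or 35+965. With 34 positives it stays at or above 80% from 416 negatives upward.

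The cost is protocol wording and two or three more positives, with the total unchanged at 1,000. Thirty-five positives keep the type I error for the positive rate below 2.5%; 34 do not. The cost rises if 99% is optimistic: at a true 97%, power for the positive rate is 38%, 73% and 81% with 32, 34 and 50 positives.
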